7.2 Rationale for Study Design

To reduce bias this study was designed as a prospective, randomized, subject- and assessor-masked study. The study IOLs are being used under approved indications for the intended population. Test procedures and inclusion/exclusion criteria will be standardized across the multiple sites and common Investigator training will be conducted.

[REDACTED]

7.3 Rationale for Duration of Treatment/Follow-Up

By 3 months post-op, refractions have typically stabilized; however, subjects will be followed for 6 months total in order to gather comprehensive effectiveness and safety data.

7.4 Rationale for Choice of Control Product

The comparator products, SYMFONY and AT LARA, are marketed EDF lenses in Australia and New Zealand.

7.5 Data Monitoring Committee

Not applicable.

8 STUDY POPULATION

The study population consists of male and female subjects (age 22 years and older) with a diagnosis of cataract requiring extraction. Approximately 218 subjects will be enrolled (consented) at up to 14 sites in Australia and New Zealand, with a target of 9-24 subjects per site. Site-specific targets may vary based upon individual site capabilities. Estimated time needed to recruit subjects for the study is approximately 6 months.

It is expected that at least 198 subjects will be randomized and at least 180 subjects will complete the study as follows:

- 60 bilaterally implanted with VIVITY
- 60 bilaterally implanted with SYMFONY
- 60 bilaterally implanted with AT LARA

This accounts for a 10% screen failure rate and a 10% rate of subjects who are not bilaterally implanted with the study IOLs or are lost to follow-up.

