1 GLOSSARY OF TERMS

Names of Test Product	AcrySof™IQ Vivity™ Extended Vision IOL, Model DFT015; throughout this document, test product will be referred to as VIVITY.
Name of Control Products	
 • TECNIS Symfony® Extended Range of Vision IOL Model ZXR00; throughout this document this control product will be referred to as SYMFONY. • AT LARA® extended depth of focus IOL Model 829MP; throughout this document this control product will be referred to as AT LARA. 
Note: Model number of device may be different if a pre-loaded delivery system is used. It should be verified by site staff that the IOL contained within matches the models listed above.

Adverse Device Effect (ADE)	Adverse event related to the use of an investigational medical device (test product) or control product. Note: This definition includes adverse events resulting from insufficient or inadequate instructions for use, deployment, implantation, installation, or operation; any malfunction; and use error or intentional misuse of the test product or control product.
Adverse Event (AE)	
Any untoward medical occurrence, unintended disease or injury, or untoward clinical signs (including abnormal laboratory findings) in subjects, users or other persons, whether or not related to the investigational medical device (test product). [REDACTED]
 
[REDACTED]
 
[REDACTED]
 
[REDACTED]
 
Requirements for reporting Adverse Events in the study can be found in Section 11.

Anticipated Serious Adverse Device Effect	Serious adverse device effect which by its nature, incidence, severity, or outcome has been identified in the risk management file.
Device Deficiency	Inadequacy of a medical device with respect to its identity, quality, durability, reliability, safety, or performance. Note: This definition includes malfunctions, use errors, and inadequate labeling. Requirements for reporting Device Deficiencies in the study can be found in Section 11.
Enrolled Subject	Any subject who signs an informed consent form for participation in the study.
Interventional Clinical Trial	A research trial that prospectively assigns, whether randomly or not, human participants or groups of humans to one or more health-related interventions to evaluate the effects on health outcomes, and/or a research trial in which diagnostic or monitoring procedures beyond standard of care are conducted and generate outcomes for use in analysis of data.

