	
Other Assessments:
 
 • [REDACTED] • Subjective manifest refraction • Biometry 
Safety:
 
 • Adverse events (including SSIs) • Device deficiencies • Surgical Problems/Other procedures at surgery • IOP • Slit-lamp exam • Dilated fundus exam • IOL Observations, IOL Position Change (tilt/decentration) • Subjective PCO assessment, Posterior Capsulotomy

Study design
	
Prospective, randomized, controlled, subject and assessor-masked, three-arm, parallel group, bilateral implant, 6-month follow-up trial of VIVITY vs. SYMFONY and AT LARA IOLs.
 <pre> graph TD A[Study Population] --> B[Adult subjects with cataract in both eyes requiring surgery and IOL implantation] B --> C[Screening/Enrollment] C --> D[Bilateral Vivity Vs. Bilateral Symphony Vs. Bilateral AT LARA] D --> E[Postoperative follow up to Visit 5A (Month 6)] E --> F[Exit visit] </pre>

Masking	 None  Observer-Masked (Examiner conducting primary and secondary effectiveness assessments [REDACTED])  Subject-Masked  Double-Masked
Subject population	Adults (22 years and older) with cataract in both eyes requiring surgery with implantation of an intraocular lens in the capsular bag. Planned number of subjects enrolled/consented: 218 Planned number of randomized/treated/implanted subjects: 198 Planned number of evaluable completed subjects: 180 
• 60 Bilateral VIVITY• 60 Bilateral SYMFONY• 60 Bilateral AT LARA
Key inclusion criteria	See Section 8.1 for a complete list of inclusion criteria
Key exclusion criteria	See Sections 8.2 and 8.3 for a complete list of exclusion criteria
Data analysis	In general, descriptive statistics will be generated using mean and two-sided 95% confidence interval, standard deviation, median, minimum, and maximum for quantitative variables and frequency and percentage for qualitative variables. Between-group comparisons for primary and secondary endpoint comparison will be conducted between the test product and each of the two comparators independently using a two sample test of proportions. [REDACTED] [REDACTED] [REDACTED] [REDACTED]

Sample size justification	Approximately 218 subjects will be enrolled to achieve 180 subjects who complete the study.      

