8.1 Inclusion Criteria

Written informed consent must be obtained before any study specific assessment is performed. Upon signing informed consent, the subject is considered enrolled in the study.

Subjects eligible for inclusion in this study must fulfill **all** of the following criteria:

[figure not shown]
[figure not shown]
Note: When criteria are ocular, both eyes must meet criteria.

1.	Adults, at least 22 years of age or older at the time of screening, of either gender, diagnosed with cataract in both eyes.
2.	Planned cataract removal by routine small incision surgery.
3.	Willing and able to complete all required postoperative visits.
4.	Able to comprehend, read and write English and willing to sign an IRB/IEC approved statement of informed consent.
█	[REDACTED]
█	[REDACTED]
█	[REDACTED]
█	[REDACTED]

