10.3 Discontinued Subjects

10.3.1 Screen Failures

Subjects who were excluded from the study after signing the informed consent and prior to randomization are considered screen failures. The Investigator must document the reason for screen failure in the subject's case history source documents.

Subject numbers must not be re-used.

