10.3.2 Discontinuations

Discontinued subjects are individuals who voluntarily withdraw or are withdrawn from the study by the Investigator after randomization.

Subject numbers of discontinued subjects must not be re-used.

Subjects may discontinue from study or study treatment at any time for any reason. Subjects may also be discontinued from study treatment at any time if, in the opinion of the Investigator, continued treatment poses a risk to their health.

If a subject discontinues from study treatment, every effort must be made to keep the subject in the study and to continue with the study assessments as specified in the schedule of study procedures and assessments until the final visit.

The Investigator must document the reason for study or treatment discontinuation in the subject's case history source documents.

To ensure the safety of all subjects who discontinue early, Investigators must assess each subject and, if necessary, advise them of any therapies and/or medical procedures that may be needed to maintain their health.

10.3.3 Schedule of Procedures and Assessments for Subjects Discontinued from Investigational Product

Subjects who discontinue IP (ie, have study lens explanted), will continue in the study through Visit 5A and be followed for safety. At minimum, safety examinations must include the assessments associated with appropriate medical care. Standard post-surgical assessments are bulleted below:

- UCDVA and/or BCDVA
- Slit-lamp Examination
- Dilated Fundus Examination

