3.1 Subject Disposition

A subject disposition table will be presented that displays the number of subjects enrolled in addition to the number of screen failures, as well as the number subjects treated, completed, and discontinued. This table will also contain counts for each reason for premature study discontinuation. A corresponding listing of reasons for early study discontinuation will also be provided.

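### Do the planned counts of 218, 198 and 180 fail to match the 10% and 10% losses they are said to cover?

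*Protocol*

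**What the plan says.** Protocol section 3 (Subject population) gives the counts: "Planned number of subjects enrolled/consented: 218 Planned number of randomized/treated/implanted subjects: 198", followed by 180 evaluable completers, 60 in each of three arms. Section 8 repeats them, with 218 given as approximate: "It is expected that at least 198 subjects will be randomized and at least 180 subjects will complete the study". It then explains them: "This accounts for a 10% screen failure rate and a 10% rate of subjects who are not bilaterally implanted" with the study lenses or are lost to follow-up. Neither rate is given a denominator.

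Other sections suggest what the denominators would be. The glossary defines an enrolled subject as "Any subject who signs an informed consent form for participation in the study", and section 8.1 agrees. Section 10.3.1 says "Subjects who were excluded from the study after signing the informed consent and prior to randomization are considered screen failures". Section 10.3.2 says "Discontinued subjects are individuals who voluntarily withdraw or are withdrawn from the study by the Investigator after randomization". SAP section 3.1 plans a disposition table that "displays the number of subjects enrolled in addition to the number of screen failures".

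Protocol section 12.8 and SAP section 7 give only the step from about 218 enrolled to 180 completing. The text after that sentence in Protocol section 12.8 is redacted.

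**The concern.** A screen failure rate is normally a share of those who consented, and a later loss rate a share of those randomised. The definitions in sections 8.1, 10.3.1 and 10.3.2 fit that reading. On those bases, 10% followed by 10% from 218 leaves fewer than 198 and fewer than 180, although section 8 gives both of those counts as minimum expectations.

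In the visible text this sentence is the only link from 218 to 180. If the stated attrition does not lead to the stated number of completers, the trial might be expected to finish below its target of 60 per arm, with some loss of precision in each comparison of VIVITY with a control lens.

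**Working it through.** **Inputs.** 218 consented, 198 randomised and 180 completing (Protocol sections 3 and 8); 10% and 10% (Protocol section 8). The bases, consented for the first rate and randomised for the second, are inferred from Protocol sections 10.3.1 and 10.3.2.

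**1. Reproducing the plan's counts.** Add 10% at each step, working back from completers:
- 180 × 1.10 = 198
- 198 × 1.10 = 217.8, which rounds to 218

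Both counts are recovered. Here 10% is 18/180 and 20/198 (10.1%), that is, relative to the smaller number.

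**2. Losses implied on the conventional bases.**
- Consent to randomisation: (218 − 198)/218 = 20/218 = 9.17%
- Randomisation to completion: (198 − 180)/198 = 18/198 = 9.09%
- Overall: 38/218 = 17.4%, against 1 − 0.90 × 0.90 = 19.0%

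**3. Applying 10% and 10% forwards.**
- 218 × 0.90 = 196.2 randomised, 1.8 below 198 (0.9%)
- 196.2 × 0.90 = 176.6 completers, 3.4 below 180 (1.9%); 176.6/3 = 58.9 per arm
- Starting from the stated 198 instead: 198 × 0.90 = 178.2, 1.8 below 180

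**4. Counts that true 10% losses would require.** 180/0.90 = 200 randomised; 200/0.90 = 222.2, so 223 consented. That is 2 more randomised (1.0%) and 5 more consented (2.3%) than planned.

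**5. Size against chance.** Assume that each consented subject completes independently with probability 0.90 × 0.90 = 0.81.
- The standard deviation of the number completing is √(218 × 0.81 × 0.19) = 5.8, so the 3.4 shortfall is about 0.6 of a standard deviation.
- The binomial probability of 180 or more completers from 218 is 0.31 at 10% and 10%. At 9% and 9% (probability 0.91 × 0.91 = 0.8281) it is 0.58.

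**6. Effect on precision.** The standard error of a difference in proportions scales with 1/√n. With 58.9 per arm in place of 60 it grows by a factor of √(60/58.9) = 1.009, about 1%. The effect on power cannot be computed, because the power assumptions are not visible.

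**The case for a change.** The case for a correction is fair. A rate of subjects failing screening or being lost is, in ordinary use, a share of those at risk. A mark-up on the smaller, later number is not such a rate, and showing that it reproduces the counts does not make the sentence accurate. Describing 218 as approximate does not rescue the second step, which starts from 198 and still falls short at 178.2. Both implied rates round to 9%, not 10%. Anyone comparing observed attrition with plan would take 10% as the benchmark. Changing one sentence would cost almost nothing.

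The arithmetic in that case stands. Three things limit what follows from it.

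First, the denominators are inferred. Section 10.3.2 concerns withdrawal after randomisation, which is not quite the category of non-implantation or loss to follow-up in section 8. Section 3 also labels the 198 as randomised, treated and implanted together, while section 8 counts non-implantation as a loss after that point.

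Second, the benchmark argument is slight. A 10% loss among 198 randomised subjects would leave the trial fewer than 2 short of 180.

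Third, rewording the rates as 9% would not clearly improve the plan. The only attrition the documents state is 10%, and lowering it would fit the assumption to the counts without evidence that less loss is expected.

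**Conclusion.** On the conventional bases the sentence in Protocol section 8 is loosely worded, and its two rates correspond to about 9.2% and 9.1%. This is a clerical matter, most simply read as a 10% allowance added at each step. The visible text does not confirm that derivation.

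The consequence is an expected shortfall of 1.8 randomised and 3.4 completing subjects, about 1 completer per arm and about 1% in the standard error. Ordinary variation in attrition is larger than that. The planned counts are consistent wherever they appear, and recruitment works to those counts. No visible hypothesis, significance level, analysis set or success rule depends on the rates. Changing the sentence would alter no target and no result, so no change is called for.

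The conclusion assumes consented and randomised subjects as the bases and, for the probabilities, independent losses. It makes no statement about power.

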8.1 Inclusion Criteria

Written informed consent must be obtained before any study specific assessment is performed. Upon signing informed consent, the subject is considered enrolled in the study.

Subjects eligible for inclusion in this study must fulfill **all** of the following criteria:

[figure not shown]
[figure not shown]
Note: When criteria are ocular, both eyes must meet criteria.

1.	Adults, at least 22 years of age or older at the time of screening, of either gender, diagnosed with cataract in both eyes.
2.	Planned cataract removal by routine small incision surgery.
3.	Willing and able to complete all required postoperative visits.
4.	Able to comprehend, read and write English and willing to sign an IRB/IEC approved statement of informed consent.
█	[REDACTED]
█	[REDACTED]
█	[REDACTED]
█	[REDACTED]

8.2 Exclusion Criteria

Subjects fulfilling **any** of the following criteria (holistically or in either eye) are not eligible for participation in this study.

1.	
Women of childbearing potential, defined as all women who are physiologically capable of becoming pregnant and who are not postmenopausal for at least 1 year or are less than 6 weeks since sterilization, are excluded from participation if any of the following apply:
 
a. they are currently pregnant,b. have a positive urine pregnancy test result at Screening,c. intend to become pregnant during the study period,d. are breast-feeding. 
[Redacted]

2.	
Any disease or pathology, other than cataract, that (in the expert opinion of the Investigator) is expected to reduce the potential postoperative best corrected distance visual acuity [Redacted]
 
[Redacted]

█	
[Redacted]

█	
[Redacted]

8.4 Rescreening of Subjects

Rescreening of subjects is not allowed in this study.

9 TREATMENTS ADMINISTERED

9.1 Investigational Product(s)

Test Product(s):

[figure not shown]
ACRYSOF IQ VIVITY Extended Vision IOL
Model DFT015

Control Product(s) (If applicable):

TECNIS SYMFONY Extended Range of Vision IOL
Model ZXR00

AT LARA extended depth of focus IOL Model
829MP

[figure not shown]
Table 9-1 Test Product

Test Product
	
ACRYSOF IQ VIVITY Extended Vision IOL Model DFT015
 
(All dimensions in millimeters)
 

Manufacturer
	
Alcon Laboratories, Inc. [name]

Indication for use and intended purpose in the current study
	
The VIVITY IOL is intended for primary implantation for the visual correction of aphakia in adult patients with < 1.00 D of preoperative corneal astigmatism, in whom a cataractous lens has been removed by extracapsular cataract extraction. The VIVITY IOL is intended for capsular bag placement only. It is also indicated for refractive lens exchange.

Product description and parameters available for this study	
 • Optic Type: Biconvex wavefront focusing optic • Optics Material: Ultraviolet and blue light filtering Hydrophobic Acrylate/ Methacrylate Copolymer • Optic Powers: 15.0 to 25.0 D in 0.5 D steps • Index of Refraction: 1.55 • Haptic Configuration: STABLEFORCE™ Modified L-Haptics • Haptic Material: Ultraviolet and blue light filtering Hydrophobic Acrylate/ Methacrylate Copolymer (Boettner 1962) • Optic Diameter (mm): 6.0 • Overall Length (mm): 13.0 • Haptic Angle: 0°
Formulation	N/A
Usage	IOLs are implantable medical devices and are intended for long-term use over the lifetime of the pseudophakic subject.
Packaging description	
Each IOL will be individually packaged and will have a unique serial number. The IOL package will contain the following items:
 
 • The IOL • A subject registration card (Lens Implant Card) • A subject identification card • Adhesive labels containing the IOL information and unique serial number • Directions on where to find the electronic package insert containing directions for product use
Labeling description	The test article will be supplied in a standard Alcon IOL carton. The carton is labeled with the following information: name of the lens, model number, overall diameter, optic diameter, diopter power, serial number, name of the manufacturer, storage conditions, expiration date, sterile, and single use. Each package is also labeled with the clinical protocol number.

Storage conditions	
Refer to product Directions For Use.
 
The VIVITY consignment provided for the study must be stored in a safe, secure location with limited access separated from general stock. Transportation of product from one address to another must be documented and a Transportation Log (or similar documentation) utilized for appropriate accountability.

Additional information	N/A
Supply	
The Sponsor will provide a consignment of test articles to each investigative site. The Investigator is responsible for maintaining the consignment, ensuring that an adequate number of IOLs are available in each dioptric power. To obtain additional IOLs, the Investigator must contact the Sponsor.

Table 9–2 Control Product Model ZXR00

Control Product(s)	
TECNIS SYMFONY Extended Range of Vision IOL Model ZXR00
  
The diagram illustrates the TECNIS SYMFONY Extended Range of Vision IOL Model ZXR00. It features two views: an Anterior Side view on the left and a Posterior Side view on the right. The Anterior Side view shows a vertical, elongated lens with a textured surface. The Posterior Side view shows a circular lens with a central optic and a surrounding ring. Key features and dimensions are labeled with red arrows:
 
 Anterior Side: 
 TECNIS® IOL WAVEFRONT-DESIGNED ANTERIOR ASPHERIC SURFACE POSTERIOR ACHROMATIC DIFFRACTIVE SURFACE AND ECHELETTE FEATURE Posterior Side: 
 HAPTICS OFFSET FOR 3 POINTS OF FIXATION Dimensions: 
 13.0 mm OVERALL DIAMETER 6.0 mm OPTIC DIAMETER Other Features: 
 FROSTED, CONTINUOUS 360° POSTERIOR SQUARE EDGE
--------------------	---

Manufacturer	Johnson & Johnson Vision [name]
Indication for Use	The SYMFONY IOL is indicated for primary implantation for the visual correction of aphakia, in adult patients with less than 1.0 D of pre-existing corneal astigmatism, in whom a cataractous lens has been removed. The lens mitigates the effects of presbyopia by providing an extended depth of focus. Compared to an aspheric monofocal IOL, the lens provides improved intermediate and near VA, while maintaining comparable distance VA.
Product description and parameters available for this study	
 • Optic Type: Biconvex aspheric optic • Optics Material: Optically clear, soft foldable, UV-blocking hydrophobic acrylic • Optic Powers: For study purposes, limited to 15.0 to 25.0 D in 0.5 D steps • Index of Refraction: 1.47 • Haptic Configuration: TRI-FIX design, haptics offset from optic, one-piece lens • Haptic Material: Soft foldable, UV-blocking hydrophobic acrylic • Haptic Color: Clear • Optic Diameter (mm): 6.0 • Overall Length (mm): 13.0 • Haptic Angle: No angulation but offset from optic body
Formulation	N/A
Usage	IOLs are implantable medical devices and are intended for long-term use over the lifetime of the pseudophakic subject.

Packaging description
	
Each IOL will be individually packaged in manufacturer’s packaging and will have a unique serial number. The IOL package will contain the following items:
 
 • The IOL • A subject registration card (Lens Implant Card) • A subject identification card • Adhesive labels containing the IOL information and unique serial number • A package insert containing directions for use

Labeling description
	
This control article will be supplied in a standard Johnson & Johnson Vision IOL carton. The carton is labeled with the following information: name of the lens, model number, overall diameter, optic diameter, diopter power, serial number, name of the manufacture, storage condition, expiration date, sterile, and single use.

Storage conditions
	
Refer to product Directions For Use.
 
Once an IOL is designated for study use, it is considered IP and must be stored in a safe, secure location with limited access separated from general stock. Transportation of product from one address to another must be documented and a Transportation Log (or similar documentation) utilized for appropriate accountability.

Additional identifying information
	
N/A


Supply
	
The Investigator will procure this control product. [REDACTED].

Table 9-3 Control Product Model 829MP

Control Product(s)	AT LARA extended depth of focus IOL Model 829MP 
Manufacturer	Carl Zeiss Meditec AG [name]
Indication for Use	The AT LARA IOL is indicated for implantation for the visual correction of aphakia in patients with and without presbyopia in whom a cataractous lens has been removed by extracapsular cataract extraction, and aphakia following refractive lensectomy in presbyopic patients.

Product description and parameters available for this study	
 • Optic Type: Diffractive aspheric • Optics Material: Hydrophilic acrylic (25%) water content with hydrophobic surface properties • Optic Powers: For study purposes, limited to 15.0 to 25.0 D in 0.5 D steps • Index of Refraction: 1.49 • Haptic Configuration: 4-haptic • Haptic Material: Hydrophilic acrylic (25%) water content with hydrophobic surface properties • Haptic Color: Clear • Optic Diameter (mm): 6.0 • Overall Length (mm): 11.0 • Haptic Angle: 0° plate haptic
Formulation	N/A
Usage	IOLs are implantable medical devices and are intended for long-term use over the lifetime of the pseudophakic subject.
Packaging description	
Each IOL will be individually packaged in manufacturer's packaging and will have a unique serial number. The IOL package will contain the following items:
 
 • The IOL • A subject registration card (Lens Implant Card) • A subject identification card • Adhesive labels containing the IOL information and unique serial number • A package insert containing directions for use
Labeling description	
This control article will be supplied in a standard Zeiss IOL carton. The carton is labeled with the following information: name of the lens, model number, overall diameter, optic diameter, diopter power, serial number, name of the manufacture, storage condition, expiration date, sterile, and single use.

Storage conditions	Refer to product Directions For Use. Once an IOL is designated for study use, it is considered IP and must be stored in a safe, secure location with limited access separated from general stock. Transportation of product from one address to another must be documented and a Transportation Log (or similar documentation) utilized for appropriate accountability.
Additional identifying information	N/A
Supply	The Investigator will procure this control product. [REDACTED] [REDACTED]

[REDACTED]
[REDACTED]

[REDACTED]
[REDACTED]

[REDACTED]
[REDACTED]
[REDACTED]

[REDACTED]

- | [REDACTED]
- | [REDACTED]
- | [REDACTED]

[REDACTED]
[REDACTED]

- | [REDACTED]
- | [REDACTED]

[REDACTED]
[REDACTED]
[REDACTED]

[REDACTED]

